After preparation of the skin with isopropyl alcohol followed by Chloraprep One-Step (2% chlorhexidine gluconate and 70% isopropyl alcohol), the two investigational PDT glucose sensing cannulas will be inserted subcutaneously in the abdomen, each at least 5 cm from the subject's insulin cannula and at least 5 cm from one another. For subjects allergic to Chloraprep, isopropyl alcohol will be used. The study investigator (PI or co-investigator, i.e. physician or nurse practitioner who has been trained in internal medicine) will manually insert each cannula into the subcutaneous tissue or will insert the cannula with the aid of a spring-operated insertion device. To ensure proper cannula insertion, a written manual and direct in-person training

(including troubleshooting) will be provided by Pacific Diabetes Technologies. The rigid stainless steel cannula will extend 12 mm into the tissue at a 35-45 degree angle (depth beneath skin surface, approximately 7-8 mm). After insertion, a small amount of saline (0.5 ml) will be delivered through each cannula to verify patency. In between usages, the insertion device will be thoroughly cleaned with SaniCloth AF-3 wipes.

The cannula is attached to a sensor housing unit which is affixed to the skin with acrylate-based adhesive tape. An Electronic Module which includes a telemetry unit is connected to the sensor housing. In between use on study subjects, the reusable telemetry unit will be thoroughly cleaned with SaniCloth AF-3 disinfecting wipes. After insertion, the subject will be instructed to avoid vigorous activity until the sensing cannula is removed at the end of the study. The subject will also be asked to keep the device dry. Sensor data (electrical current proportional to glucose level) will be stored within the body-worn electronic module at least once every minute. Sensor data from these investigational sensors will not be used to control the FMPD single hormone algorithm or insulin dosing at any time. The subject will not be able to view the sensor output. A visual analog scale and questionnaire will be given to assess tolerability and pain of the glucose sensing cannulas at 15 and 120 minutes after insertion and just before the glucose sensing cannulas are removed at the end of the study (see Appendix D).

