One t:slim infusion pump (Tandem® Diabetes Care) will be filled with lispro insulin and another will be filled with normal saline. Each pump will be attached to one of the PDT sensing cannulas. See **Figure 2** below for a diagram of the system design. Subjects will disconnect his/her own pump and remove his/her own insulin infusion set once insulin delivery has started via the t:slim pump. Note: The Zephyr Biopatch will not be used in this study to push heart rate data into the APC system to enable exercise detection.

Figure 2: Closed-loop System Design

An 18-22 gauge IV catheter will be placed for measuring blood glucose concentration. When closed loop study is started, a small amount of blood will be collected every 15 minutes until discharge from the unit at 6pm. A heating pad will be placed on the subject's arm to facilitate blood draws and to arterialize venous blood, which allows for frequent measurement of blood glucose and to prevent spurious decline of venous blood glucose from glucose uptake by muscle and fat during slow capillary flow. These arterialized venous samples will be analyzed using a Yellow Springs Instrument (YSI) 2300D Stat Plus Analyzer to obtain a glucose level. In the event the YSI is not available, the sample will be analyzed using a Contour Next blood glucose meter. Normal saline will be infused at a rate of ~25 ml/hr to keep the IV catheter patent. It is possible that the IV catheter will not remain patent, in which case another will be placed. In a blood-sparing technique, venous blood will be withdrawn from the IV catheter using a double stop-cock method. One side of the stop-cock is used to pull ~ 5 mL of saline-blood admixture. The other side of the stop-cock is used to pull approximately 0.5 ml for collection with the saline-blood admixture re-infused after collection. The double stop-cock method is a fully closed system apart from the very brief interval at the time of a blood sample where a new sterile syringe is connected to collect the next sample. This procedure is performed by a research nurse. There will be ~18-20 ml of blood collected per study with a maximum blood draw volume of 30 mL.

After the Dexcom G5 warm-up period is completed, the research staff will initialize the system and begin the closed-loop study. The second t:slim pump will deliver normal saline at the same rate as the insulin pump. The study investigator will then depart but remain on call.

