electrical current in nanoamperes (nA). We will match these sensor values with YSI values which are in units of mg/dL. We will then do a linear least squares regression between the YSI glucose and the sensor current to create an equation that estimates the actual glucose from the sensor current. This equation will have the form of $y=mx + b$, whereby y is the estimated glucose (mg/dL), m is the slope (mg/dL/nA), x is the current measured by the sensor (nA), and b is the intercept or background current (nA). The slope and intercept will be estimated for each patient and for both the saline sensing catheters and the insulin sensing catheters. We will then do a t-test between the slopes and the intercepts comparing these values between the saline sensing catheters and the insulin sensing catheters. The hypothesis is that the null hypothesis (the mean value of both the slope and intercept values are identical between the saline and insulin sensing catheters) is true which will be estimated by a p-value being greater than 0.05.

Another key end point will be glucose sensor accuracy (absolute difference, relative difference, and absolute relative difference) during insulin vs during saline delivery. These metrics will be calculated by using two types of calibration schemes: a one-point calibration with fixed offset, performed prospectively before meal administration, as described earlier [21]; and a retrospective all point calibration as proposed for early device evaluation, as proposed by Heinemann and Ludwig [22]. In addition to mean and median absolute difference, mean and median relative difference, and mean and median absolute relative difference, other accuracy metrics will include signed difference (bias). Error grid analyses will include Clarke, Parkes and continuous analyses. Bland-Altman analysis will be used to stratify accuracy as a function of glucose level.

In addition to the glucose sensing data described above, the subjects enrolled in the proposed clinical study will be asked to provide tolerability scores, which will include visual analog scales, to assess their level of comfort. During the study, skin irritation (Draize scores) will also be recorded. The tolerability and Draize scores will provide key data that will be used to support subsequent device modifications that reduce discomfort and skin irritation.

Confidentiality and Protection of Human Subjects

RISKS and BENEFITS

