NOTE -- the non-sterile devices indicated below will be sanitized with SaniCloth AF-3 wipes prior to use.

Prepare Devices

Physician dons gloves and prepares a sterile field. She carries out the steps listed below.

1. Remove from the sterile 50 mL vial the CGM insulin infusion set. Separate the insulin infusion tubing (Panel 1) from the sensor housing (Panel 2) by pressing the outer arms of the quick connector (Panel 1). Place the insulin infusion tubing on sterile field.
2. Place the sensor housing on the non-sterile loading base being careful to avoid contaminating the sterile cannula.
3. Place the non-sterile insertion device (Panel 5) over the loading base and press down. This action loads the sensor housing into the insertion device.
4. Cock the insertion device and set it aside for later use. Set aside the loading base for later use.

Insert cannula

5. Prepare the skin site with isopropyl alcohol pad(s) in ever-widening circles.
6. Remove the upper and lower liners from the non-woven adhesive patch.
7. Place the non-woven bandage on to the skin surface so that the skin worn device is oriented horizontally (left-right) on the body, not vertically.
8. Align the loaded inserter on to the non-woven bandage, then activate the inserter (insert cannula through skin). Visually verify that the cannula is in the tissue.
9. Remove the inserter and set aside

[figure not shown]
Insert and Anchor Electronic Module

10. Remove the electronic module (Panel 7) from the charger (Panel 6).
11. Using the laptop program, verify connectivity to the Bluetooth electronic module, then connect the electronic module to the sensor housing as shown in Panel 4. The electronic module will automatically start transmitting repeated “Active Status” signals to the laptop computer.
12. Apply polyurethane overbandage (such as Tegaderm), being careful to leave space for mating of quick connector to sensor housing.

Attach Insulin Pump and Fill the Insulin Fluid Path (Prime)

13. Connect reservoir to Tandem t:slim insulin pump. Avoid touching the sterile recessed reservoir-connection needle.
14. Using the pump interface, prime insulin line until insulin liquid is seen dripping through needle on quick connector. Avoid touching the sterile recessed quick connector needle.
15. Attach the quick connector to the sensor housing.
16. Using the pump interface, carry out the needle prime (0.7 units) to fill the cannula with insulin.

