APPENDIX E: DRAIZE SCALE

To be completed by the person who removes the devices (PI, Co-I, or clinical coordinator)

Sensing Cannula (LEFT)

DRAIZE SCALE At END OF VISIT	 0=No erythema  1=Very slight, barely perceptible erythema  2=Well defined erythema  3=Moderate erythema  4=Severe erythema, Beet redness to slight eschar formation	 0=No edema  1=Very slight, barely perceptible edema  2=Well defined edema  3=Moderate edema, raised approx. 1mm  4=Severe edema, raised >1mm and beyond exposure area
---	---	---

Sensing Cannula (RIGHT)

DRAIZE SCALE At END OF VISIT	 0=No erythema  1=Very slight, barely perceptible erythema  2=Well defined erythema  3=Moderate erythema  4=Severe erythema, Beet redness to slight eschar formation	 0=No edema  1=Very slight, barely perceptible edema  2=Well defined edema  3=Moderate edema, raised approx. 1mm  4=Severe edema, raised >1mm and beyond exposure area
---	---	---

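### In the visible text, no random or balanced rule decides which of a subject's two sensing cannulas carries lispro, so a consistent side, insertion-order or selection difference would be confounded with the lispro-saline comparison

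*Combined protocol and SAP*

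**What the plan says.** The Primary Objectives and Study Type sections set up a lispro-versus-saline comparison of sensing in 10 subjects. Each subject wears both cannulas during one visit, so the choice of cannula for each fluid is the treatment assignment.

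The section on the 12 hour Treatment Visit gives these steps:

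- **Placement.** Both cannulas go into the abdomen, each at least 5 cm from the subject's "insulin cannula and at least 5 cm from one another". Insertion length and angle range are common to both, and the inserters are trained.
- **Insertion.** The investigator will "manually insert each cannula into the subcutaneous tissue or will insert the cannula with the aid of a spring-operated insertion device".
- **Check.** "After insertion, a small amount of saline (0.5 ml) will be delivered through each cannula to verify patency".
- **Connection.** One pump holds lispro and the other saline. "Each pump will be attached to one of the PDT sensing cannulas".
- **Own pump.** Subjects disconnect their own pump and "remove his/her own insulin infusion set once insulin delivery has started via the t:slim pump".

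The insertion steps in Appendix C include "Visually verify that the cannula is in the tissue" (step 8) and a laptop connectivity check (step 11). Both come before the infusion line is attached (step 15).

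The tolerability and Draize forms are scored by side, for example "Sensing Cannula (LEFT)". The printed forms do not say which side carried which fluid.

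For the analysis, Data Analysis says "We will then do a t-test between the slopes and the intercepts", comparing saline with insulin catheters. It mentions neither side nor insertion order, and it treats a p-value above 0.05 as support for the hypothesis of no difference.

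**The concern.** Nothing in the visible text says who decides which cannula receives lispro, when, or by what rule. Pairing removes differences between subjects, but not differences between the two positions within a subject.

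Three kinds of position difference remain possible:

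- **Side or order.** Staff might habitually connect lispro to the same side, or to the first cannula inserted.
- **Method.** The text does not require both cannulas in a subject to be inserted the same way.
- **Selection.** If both cannulas are in place before either line is attached, staff could give the better-looking one to a particular fluid. They would know the visual placement, the patency flush and the connectivity check. The documents do not say whether both are in place first; Appendix C reads as a sequence for one device at a time.

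A consistent difference of any of these kinds would go straight into the estimated lispro effect on slope and intercept. The bias can run either way. If it opposes a real lispro effect, it pushes the p-value above 0.05, which the plan would read as no impact. If there is no lispro effect, it can create an apparent one.

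**Working it through.** **Is there a rule?** In the visible text, randomisation appears only in descriptions of other studies (Background and References). No alternating, counterbalanced or fixed rule is stated. The plan's sample size of 10 cannot be reproduced, because the Power Analysis section says the variance is unknown and the study is not powered.

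**Inputs.** From the documents: n = 10 pairs and a 0.05 threshold. Assumed, because the documents do not say: the t-test is paired and two-sided, and differences are normal. Effects are in SDs of the within-subject difference; the site effects s and the 1.0 SD lispro effect are illustrations. Error rates are per test.

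**Lispro always on the same side.** The mean difference is (lispro effect + s). The test statistic is noncentral t with 9 degrees of freedom, noncentrality δ√10 and critical value 2.262. With no lispro effect, δ = s. With a 1.0 SD lispro effect that the site effect opposes, δ = 1 − s. For example, s = 0.5 gives noncentrality 0.5 × 3.162 = 1.581 in both cases, hence 0.293 in both columns.

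| Site effect s (SD) | P(p < 0.05), no lispro effect | Power, opposing 1.0 SD lispro effect |
|---|---|---|
| 0 | 0.050 | 0.803 |
| 0.25 | 0.109 | 0.562 |
| 0.5 | 0.293 | 0.293 |
| 1.0 | 0.803 | 0.050 |

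**Side chosen purely by chance.** With a coin flip per subject and a plain paired t-test, expected bias is zero. Simulated overall error is 0.05 at site effects of 0.25, 0.5 and 1.0 SD. A split of 8:2 or worse occurs with probability 2 × (45 + 10 + 1)/1024 = 0.109, which is a reason to prefer a balanced list to a coin flip.

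**Balanced list with a side term.** Model the within-subject difference as d = L + s·x + error, with x = +1 for lispro-left and −1 for lispro-right. The intercept L is the lispro effect. For a 1.0 SD lispro effect the noncentrality is √(n(1 − x̄²)), with n − 2 degrees of freedom.

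- At 5:5, x̄ = 0, the noncentrality is 3.162 with 8 degrees of freedom, and power is 0.791. Simulated error is 0.049 to 0.051 at site effects of 0, 0.5 and 1.0 SD.
- If balance is left to chance and the term is added later, power is 0.719 at 7:3, 0.603 at 8:2 and 0.386 at 9:1. At 10:0 the two effects cannot be separated.
- A 5:5 list without the side term is unbiased but rejects too rarely when a site effect exists: 0.030 at 0.5 SD and 0.007 at 1.0 SD with no lispro effect.

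**MAD and MARD.** These are the listed primary endpoints, and the table above does not apply to them. If each catheter is calibrated separately, a pure sensitivity difference between sites is largely absorbed, while a difference in noise or lag is not. The documents do not allow the size to be derived.

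**The case against.** The strongest reply has four parts.

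1. **A rule may exist out of sight.** Figure 2, the insertion manual and the visit CRF are not shown. This stands: a random or balanced rule in any of them would answer the point. A fixed side stated there would not, because it would leave side and fluid fully confounded.
2. **No habit is shown.** A reader might infer that lispro was always placed on one side, or that the better cannula was picked for one fluid. The documents do not support either reading; they leave the choice open. If side is chosen independently of site quality, there is no expected bias and error stays near 0.05. Material bias needs a consistent habit or selection.
3. **The site effects are assumed, and the plan limits them.** Region, insertion length, angle range, training and delivery rates are common to both cannulas. A full 1.0 SD shift is an extreme illustration. The subject's own pump is also a weak mechanism: its set comes out once t:slim insulin delivery starts, and the 15-minute reference sampling starts with closed loop. That leaves mainly residual insulin at least 5 cm away.
4. **The study is exploratory and not powered.** That excuses imprecision. It does not excuse a bias that is nearly free to prevent, especially as Data Analysis still tests a hypothesis and plans to use these data to power later studies. An unmodelled side effect with mixed sides would inflate that variance.

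**Conclusion.** The point holds as a gap in protection. The visible plan has no random or counterbalanced assignment of fluid to cannula and no side term, so a consistent position difference could not be told apart from a lispro effect on slope or intercept.

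The size cannot be derived from the documents, and its lower bound is zero. The illustrative range is an error of 0.11 to 0.80 instead of 0.05, for assumed site effects of 0.25 to 1.0 SD with lispro always on the same side. Those figures concern the slope and intercept t-tests only. An effect on MAD/MARD is possible but unquantified, so it would be wrong to read the figures as error rates for the listed primary endpoints.

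The change is worth making because it is cheap and protects the primary contrast. It does not settle the separate question of whether p > 0.05 can be read as no effect.

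**What to change.** 1. **Allocate.** Prepare a balanced random list before the first visit: five subjects lispro-left and five lispro-right. Open each entry only after both cannulas are inserted and flushed. If devices are completed one at a time, open it after both sites are chosen; this is weaker, because it protects the choice of site but not what happens during insertion.
2. **Record.** On the visit CRF, enter fluid, side, insertion order and insertion method for each cannula. The list balances side exactly; insertion order is balanced only if it follows side, so it must be recorded.
3. **Analyse.** Fit the within-subject differences in slope and intercept with a ±1 side term, and report the intercept as the lispro effect.

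If a balanced rule already exists in the insertion manual or CRF, state it in the protocol and add the side term.

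The cost is a 10-line list, a few CRF fields, one model term and perhaps a small change in the order of attachment. No subjects or procedures are added. The side term uses one degree of freedom: power for a 1.0 SD effect falls from 0.80 to 0.79 at 5:5. If a withdrawal leaves 5:4, it is 0.73, mainly because of the smaller n. The rule has to be in place before the first connection, because a later side term cannot rescue a 10:0 split and cannot correct selection of the better-looking cannula.
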